## 9.2

This figure is a 2D bar chart consisting of several horizontal bars. The bars are black and are set against a white background. The lengths of the bars vary, with some being significantly longer than others. The bars are arranged in a staggered, non-overlapping pattern, creating a sense of depth. The overall composition is minimalist and abstract.

24

---

CONFIDENTIAL  
Sight Sciences

Adverse events may occur intra-operatively or post-operatively.

### **9.3 REPORTING ADVERSE EVENTS AND UNANTICIPATED ADVERSE DEVICE EFFECTS**

Identification, collection and reporting of adverse event information is the responsibility of the Principal Investigator. The Investigator records the date of the event, its severity, treatment (if any) and the assessed relationship of the event to the study device on the AE CRF.

Any ocular **serious adverse event (SAE)** should be reported to the study sponsor within one business day of learning of the event. Non-ocular SAEs should be reported to the study sponsor within two working days of learning of the event. Enter data in electronic data capture (EDC) system within two working days of learning of the event.

Any **unanticipated adverse device effects (UADE)** must be reported to the following two entities:

1. The study sponsor – Within one working day of the investigator first learning of the event enter data in EDC; and
2. The reviewing IRB – As soon as possible, but no later than 10 working days after the investigator first learns of the event, report per the IRB's instructions.

The sponsor will conduct an evaluation of unanticipated adverse device effects. If the sponsor determines that an unanticipated adverse device effect presents an unreasonable risk to subjects, parts of the investigation presenting risks will be terminated. Termination will occur no later than 5 working days after the sponsor

makes such a determination and no later than 15 working days after the sponsor first received notice of the effect.

## 10 STATISTICAL CONSIDERATIONS

### 10.1 SAMPLE SIZE CALCULATION

This is a descriptive study and is not designed to test pre-planned hypotheses. The sample size is based on an understanding of the approximate number of eligible patients available at the participating sites and not on formal sample size calculation. With an assumed standard deviation of 3.5 mmHg for intraocular pressure, a minimum change in IOP of 5.0 mmHg from a pre-operative baseline of mean = 21 mmHg, and alpha = 0.05, a sample size of minimum 50 subjects is required to get at least 90% power to detect statistical significance.

With a total sample size of up to 130, adverse events with a frequency of approximately 3% would be detected with 97.5% probability.

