### **8.3 NUMBER OF SUBJECTS, DURATION OF FOLLOW-UP AND STUDY DURATION**

Up to 130 subjects will be enrolled. Eligible subjects will be enrolled at the 24-month follow up timepoint as shown by Table 1 or 2 as applicable. At least 50 subjects will be enrolled in each cohort. For subjects in cohort A, diurnal IOP measurements will be measured at both visits for those subjects who underwent medication washout and where DIOP was measured pre-operatively (Cohort A). Cohort A subjects using ocular hypotensive medication(s) at 24 and 36 months will undergo a medication washout (Table 3) and return for diurnal IOP measurements at a second visit within the same window, as shown in Table 1. There will be no diurnal IOP measurements for subjects in cohort B. IOP measurements will be measured as shown in Table 2.

It is anticipated that site initiation, recruitment and follow-up of subjects, data collection and site close-out will require approximately 60 months.

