## 10.4 EFFECTIVENESS ENDPOINTS AND ANALYSIS METHODS

Descriptive statistics on continuous variables will include mean, standard deviation, median, minimum, and maximum. Confidence intervals for change from baseline will be included for selected endpoints. Categorical variables will be summarized using frequency counts and percentages. Exact confidence intervals for point estimates may be provided. Statistical testing will be one-sided with a significance level of 0.025 or two-sided significance level of 0.05 unless specified otherwise. Data listings of individual subject data may be provided.

Subjects with washout and those without washout will be analyzed separately.

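### Section 10.1 says at least 50 subjects are required for 90% power, but its own inputs need about 8 to 13 and at most 23 in a paired t-test

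*Combined protocol and SAP*

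**What the plan says.** Section 10.1 of the combined protocol and SAP gives two accounts of the sample size. The first rests on feasibility: "This is a descriptive study and is not designed to test pre-planned hypotheses", and the number comes from the patients "available at the participating sites and not on formal sample size calculation". The second is a power statement. It starts "With an assumed standard deviation of 3.5 mmHg for intraocular pressure, a minimum change in IOP of 5.0 mmHg", takes a pre-operative mean of 21 mmHg and alpha 0.05, and concludes that "a sample size of minimum 50 subjects is required to get at least 90% power to detect statistical significance".

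Section 10.1 names no test, no sidedness, no correlation between visits and no loss rate. Section 10.4 adds: "Statistical testing will be one-sided with a significance level of 0.025 or two-sided significance level of 0.05 unless specified otherwise". Section 8.3 uses the same number as a floor: "At least 50 subjects will be enrolled in each cohort". The effectiveness endpoints in section 6.2 include reductions in IOP from the pre-operative value, and section 10.4 has the two cohorts analysed separately. The comparison behind the power statement is therefore a within-subject change in one cohort, with no control arm.

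**The concern.** A 5.0 mmHg change against an SD of 3.5 mmHg is a standardised effect of 5.0/3.5 = 1.43. Detecting an effect that large within subjects takes a handful of subjects, so a stated minimum of 50 looks wrong at once. The SD is also attached to IOP rather than to change in IOP, although a test of change depends on the SD of the change. A reader cannot tell which quantity was meant and cannot reproduce the number.

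Little is at stake for the study's conclusions, because the discrepancy runs in the safe direction. What is at stake is the accuracy of the plan: a sample-size figure is presented as following from inputs that do not produce it.

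**Working it through.** **Inputs.** From section 10.1: SD 3.5 mmHg, change 5.0 mmHg, alpha 0.05, power at least 90%, stated n = 50. From section 10.4: two-sided 0.05 or one-sided 0.025, which give the same n. The documents give no correlation between visits, so the values below are assumptions shown as a range.

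**Method.** Paired t-test with exact noncentral-t power: noncentrality = (5.0 / SD of change) × √n, with n - 1 degrees of freedom. If 3.5 mmHg is the SD at each visit, the SD of change is 3.5 × √(2(1 - ρ)).

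**Attempt to reproduce 50** (two-sided 0.05):

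| Reading of 3.5 mmHg | SD of change | n needed | Power at n | Power at n - 1 | Power at 50 |
|---|---|---|---|---|---|
| SD of change | 3.5 | 8 | 93.1% | 88.0% | >99.99% |
| Each visit, ρ = 0 | 4.95 | 13 | 91.6% | 88.9% | >99.99% |
| Each visit, ρ = -1 (extreme) | 7.0 | 23 | 90.5% | 89.1% | 99.86% |

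The normal approximation n = (SD × (1.960 + 1.282) / 5.0)² gives 6, 11 and 21 for the three rows, which agrees with the exact results apart from the usual small-sample shortfall.

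Positive correlation between readings on the same eye lowers the number: n = 10, 8, 7, 6 and 5 at ρ = 0.3, 0.5, 0.6, 0.7 and 0.8. One-sided 0.05 gives 6, 10 and 19 for the three rows.

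**What would make 50 the minimum.**

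- With a change of 5.0 mmHg, 90% power is reached at SD of change 10.58 for n = 49 and 10.69 for n = 50. So 50 is the minimum only for an SD of change of about 10.6 to 10.7 mmHg, and 10.6/3.5 = 3.0 times the stated SD.
- With SD of change 3.5, 90% power is reached at a change of 1.637 mmHg for n = 50 and 1.654 for n = 49. With SD of change 4.95 the values are 2.315 and 2.339 mmHg. None is near 5.0.
- Inflation for losses, n/(1 - d) = 50, needs d = 1 - 8/50 = 84%, 1 - 13/50 = 74% or 1 - 23/50 = 54%.
- Reading 50 as the total for two cohorts gives 2 × 8 = 16, 2 × 13 = 26 or 2 × 23 = 46.

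**What 50 per cohort delivers.** The t-based 95% half-width for the mean change is 2.01 × SD/√50, which is 0.99 mmHg at SD of change 3.5 and 1.41 mmHg at 4.95. The change detectable with 90% power is 1.64 and 2.31 mmHg respectively.

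**The case against.** The strongest reply is that the sentence does not carry the design. Section 10.1 has already said that the study tests no pre-planned hypotheses and that its size rests on available patients, so the power statement is only supporting reassurance. Its operative content is true: 50 subjects do give at least 90% power under every reading tested. All of that stands, and it is why the point is minor. It does not rescue the sentence, because calling 50 a required minimum says that fewer would not do, and on the stated inputs fewer would.

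A second reply is that 23 is not a bound over every method. That is correct: it bounds a paired t-test with an SD of 3.5 mmHg at both visits and alpha 0.05. An independent-groups t-test with equal allocation needs 24 in total. Starting from the extreme of 23, a Wilcoxon efficiency of 0.864 or alpha halved for the two cohorts each brings the number to 27. None of these is the stated plan, and none comes close to 50.

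A third reply is that the SD is not wholly undefined: the literal reading of "With an assumed standard deviation of 3.5 mmHg for intraocular pressure" is the SD of a single IOP value, and what is missing is the correlation. That is fair, and it makes 13 or fewer the more literal answer for non-negative correlations. The ambiguity is then narrower, but the SD of change still cannot be obtained from the text.

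**Conclusion.** The concern holds as a minor error. The figure of 50 does not follow from the inputs in section 10.1. Those inputs need 8 subjects (3.5 mmHg as SD of change) to 13 (SD at each visit, uncorrelated), fewer if visits are positively correlated, and at most 23 in a paired t-test with equal SDs. This rests on a within-subject test in one cohort at two-sided 0.05, which is what sections 6.2 and 10.4 imply although 10.1 does not name it. The correlations are assumptions, and no value of them gives 50.

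The error is conservative. With 50 per cohort, power for a 5.0 mmHg mean change is above 99.8% even in the extreme case, so nothing is underpowered. The faults are a stated requirement that is wrong as written and an SD that is not identified.

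**What to change.** Keep feasibility as the basis for the size. State whether 3.5 mmHg is the SD of the change or of a single IOP reading, name the test and sidedness, and replace the sentence that calls 50 required. If 3.5 mmHg is the SD of change, a suitable text is:

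*Fifty subjects per cohort exceeds the number needed for 90% power to detect a 5.0 mmHg mean change (paired t-test, two-sided alpha 0.05), and gives 90% power for a change of about 1.6 mmHg (95% CI half-width about 1.0 mmHg).*

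If 3.5 mmHg is the single-visit SD, the plan should also state the correlation it assumes. With uncorrelated visits the two figures become about 2.3 mmHg and about 1.4 mmHg, and both shrink as the correlation rises.

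The cost is one replaced sentence in section 10.1. Enrolment, the floor of 50 per cohort in section 8.3, visits and analyses stay as they are.

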### 10.2 ANALYSIS POPULATIONS

The intent-to-treat (ITT) analysis population includes all subjects who are enrolled and treated, regardless of whether or not they have a protocol deviation. The per-protocol analysis population (PP) is a subset of ITT, which includes all subjects who have canaloplasty and trabeculotomy after uneventful cataract surgery, 36-month IOP (or hypotensive medications washed out IOP if the medications can be washed out) and medication data, and have no clinically significant protocol deviations. It should be noted that the ITT subjects with an uneventful study procedure but with secondary surgical interventions (SSIs) before the 36-month visit will be included in the PP population even if they do not have the 36-month IOP and medication data.

The safety data will be summarized based on the ITT population.

### 10.3 DEMOGRAPHICS AND BASELINE CHARACTERISTICS

Demographic variables gender, race, ethnicity, and age will be summarized for all enrolled subjects treated with OMNI Surgical System, along with medical history. Descriptive statistical summaries of pre-treatment parameters (min, max, median, mean, and standard deviation) will also be provided. The same analyses will be performed for the ITT and PP populations.

## 10.4 EFFECTIVENESS ENDPOINTS AND ANALYSIS METHODS

Descriptive statistics on continuous variables will include mean, standard deviation, median, minimum, and maximum. Confidence intervals for change from baseline will be included for selected endpoints. Categorical variables will be summarized using frequency counts and percentages. Exact confidence intervals for point estimates may be provided. Statistical testing will be one-sided with a significance level of 0.025 or two-sided significance level of 0.05 unless specified otherwise. Data listings of individual subject data may be provided.

Subjects with washout and those without washout will be analyzed separately.

## 10.5 SAFETY ANALYSIS

All safety analyses will be performed on the ITT population based on all available data descriptively.

### 10.5.1 ADVERSE EVENTS

AEs will be classified as pretreatment, intraoperative or postoperative. The number and the percent of eyes reporting at least 1 adverse event of a given type will be summarized. Additionally, the number of reports of each type of AEs will be provided.

For each AE, the number and the percent of eyes reported with the event will be summarized by the severity level. For eyes with multiple reports of the same type of AE, the maximum severity will be used. Similarly, the AE relationship to the procedure will be summarized. For eyes with multiple reports of the same type of AE, the closest relationship to the procedure will be used.

### 10.5.2 BEST CORRECTED VISUAL ACUITY

The number and percent of eyes reporting with BCVA of 20/20 or better, 20/25 or better, 20/32 or better, 20/40 or better, worse than 20/40 to 20/80, worse than 20/80 to 20/200, and worse than 20/200 at each visit will be summarized. The number and percent of eyes reporting BCVA of increase  $\geq$  10 letters, increase 10 letters, increase  $\geq$  5 letters to < 10 letters, within 5 letters change, decrease  $\geq$  5 letters to < 10 letters, decrease 10 letters, and decrease  $\geq$  10 letters at each postoperative visit will be calculated.

### 10.5.3 OTHER SAFETY OUTCOMES

The number and percent of eyes reported with each kind of slit lamp findings, gonioscopy findings, and dilated fundus examination findings at each visit will be provided.

The descriptive statistics for the continuous variables will be derived for the visual field mean deviation (MD) and pattern standard deviation (PSD).

### 10.6 INTERIM ANALYSIS

An interim analysis providing descriptive statistics for the outcomes may be completed following completion of the 24-Month follow-up visit by 100% of the enrolled subjects. Endpoints listed below will be analyzed at an interim analysis. No device effectiveness will be claimed based on the interim analysis outcomes.

Subjects with washout and those without washout will be analyzed separately.

Effectiveness outcomes up to 24 months will be summarized descriptively, as follows:

1. Percent of eyes with a  $\geq 20\%$  reduction from pre-operative baseline in IOP with no increase in IOP-lowering medications compared to the pre-operative visit;
2. Percent of eyes with IOP between 6 and 18 mmHg with no increase in IOP-lowering medications compared to pre-operative visit;
3. Percent of eyes with IOP between 6 and 21 mmHg with no increase in IOP-lowering medications compared to pre-operative visit;
4. Mean reduction in DIOP from the pre-operative DIOP (Cohort A), or Mean reduction in medicated IOP from the pre-operative medicated IOP (Cohort B); and
5. Reduction in mean number of IOP-lowering medications from the pre-operative visit.

The primary safety endpoint is the rate of occurrence of sight-threatening AEs.

The secondary safety endpoints are the rates of ocular adverse events, the reduction in BCVA from baseline, and secondary ocular surgical interventions, including laser, for IOP control.

### 10.7 DEVIATION FROM THE STATISTICAL PLAN

Any deviations from the statistical plan will be noted in the final report.

## 11 MONITORING PROCEDURES

Sight Sciences, Inc. ("Sight") or contract research organization (CRO) personnel will monitor the study in a manner consistent with FDA regulations, good clinical practices (GCPs), and the clinical research standards adopted by Sight. Study monitoring will be executed using on-site and remote monitoring visits as needed and as determined by the study team. The frequency and necessity of visits will be determined by the study team. Study monitoring will involve the following elements:

- **Site Qualification:** Sight or CRO personnel will meet with investigators and clinical study staff prior to the initiation of the study in order to review the adequacy of the subject population, facilities, and equipment with respect to the needs of the study, and to familiarize the investigator with the study protocol. If Sight or the CRO have recently been involved with an investigator for another study, a site qualification visit may not be necessary.
- **Site Initiation:** Sight and/or CRO personnel will meet with the investigator(s) and clinical study staff when the site is ready to begin enrolling subjects in order to train them in how to properly select subjects, perform the study procedure, and record study data. The site initiation visit may be conducted remotely and may include a grouping of multiple sites. This visit will include, but not be limited to a review of the following:
  - Detailed review of the protocol;
  - Informed consent procedures;
  - Instructions for the surgical procedure; and
  - Records and reports.
- **Interim Monitoring:** Sight or CRO personnel will conduct routine visits during the course of the study to review charts, perform source document verification, ensure proper adherence to the study protocol, and to review regulatory documents. Interim monitoring visits and telephone consultation will occur as necessary during the course of the study to ensure the proper progress and documentation of the study findings.
- **Study Close Out Visit:** At the conclusion of the trial there will be a study closure visit during which several actions, including but not limited to the following, will be performed:
  - A final inspection of the study binder;
  - Accountability and return of all devices and non-consumable ancillary study supplies to the sponsor;
  - Discussion of record retention requirements with the investigator; and
  - Close-out notification to the IRB.

## **12 DATA AND QUALITY MANAGEMENT**

### **12.1 DATABASE MANAGEMENT**

The study database will be designed using an electronic data capture (EDC) system that is compliant with 21 CFR Part 11 and relevant guidance documents. The EDC will be developed and maintained by an independent, qualified data management firm.

The database will incorporate time-stamped audit trails, protection of human subjects, restricted access, and data security at the component level. Each database module, including each individual electronic case report form (eCRF), will be validated by conducting a series of standard tests that demonstrate usability and correctness of the database system. The database will be maintained on an ongoing basis and will be routinely backed up.

### **12.2 SUBJECT IDENTIFICATION**

The subjects will be identified by a six-digit subject number composed of a double-digit study identification number, a two-digit center identification number followed by a two-digit sequential subject number. A subject identification number will be assigned after informed consent is obtained. This will ensure that identifiable subject information has been removed and kept confidential.

### **12.3 SUBJECT ACCOUNTABILITY**

All subjects enrolled in this clinical investigation shall be monitored for the duration of the investigation. The clinical investigation shall be considered completed when all subjects that have been enrolled in the investigation have reached the final reporting period, excluding subjects who were withdrawn.

### **12.4 CONFIDENTIALITY**

All medical records associated with the clinical investigation will be made available for review by Sight personnel, its CRO, and governmental/regulatory agencies involved. The results of the study may be published in the future for scientific and marketing purposes, but the identity of each subject will not be revealed. All records will be stored in a secure area at the investigator's facility, the CRO, the data management firm, and Sight.

## 12.5 SOURCE DATA AND CASE REPORT FORMS

Source data will be entered into a validated electronic system at each site by trained personnel in accordance with 21 CFR Part 11 requirements. Electronic entries will be verified against corresponding source data at the sites and queried/corrected if needed to the extent possible. Medical site records serve as source data. In addition, data that are collected exclusively for the purpose of this study and not normally recorded in the subjects' medical records can be collected directly on any study CRFs or tools provided by the sponsor, and these will serve as the source data.

Source data and study CRFs are to be maintained at the site in the subject records or in the medical records. All data entries must be made in accordance with ALCOA (Attributable, Legible, Contemporaneous, Original, Accurate) standards and GDP (Good Documentation Practices).

Study data acquired from sites will be collected on eCRFs for submission to sponsor. Sites will enter data entered on source documents into the electronic case report forms for Sponsor review and analysis.

## 12.6 RETENTION PERIOD

Clinical sites are to retain any and all clinical trial material (documentation, photographs, etc.) for a period of two years from the date a marketing application is approved or two years after the investigation has been discontinued, or as directed by their institutional document retention requirements, whichever is the longest. After that time, the items must be returned to Sight for archiving.

## 13 PROTOCOL MODIFICATIONS AND DEVIATIONS

Protocol modifications may occur during the study. Each will be approved by the sponsor before implementation. Each will undergo Institutional Review Board (IRB) review and approval, as necessary.

Any deviations from this protocol intended to protect the life or physical well-being of a subject in an emergency are to be reported to Sight and the IRB as soon as possible, and no later than 5 working days after the emergency occurred.

All protocol deviations will be documented using the Protocol Deviation CRF or Source Tool.

## 14 ETHICAL CONSIDERATIONS

### 14.1 DECLARATION OF HELSINKI

This study shall be conducted in accordance with the Declaration of Helsinki (Appendix D).

### 14.2 INSTITUTIONAL REVIEW BOARDS (IRB)

The study shall not begin at a site until approval has been obtained from the reviewing IRB. It is the Investigators' responsibility to obtain and maintain written approval of the study protocol and Informed Consent documents from the appropriate IRB. It is also the Investigators' responsibility to notify and obtain approval from (if needed) that body about any amendments to these documents and to follow the IRBs rules regarding the reporting of AEs and Protocol Deviations related to the investigational device and/or this study. Copies of all written approvals (identifying the study, the submitted and approved documents and the date reviewed) and the approved versions of the documents must be provided to Sight or its CRO.

The Investigators must file all correspondence with the IRB and forward copies of such correspondence to Sight.

